6.2.1.1. Primary Analyses

The response rate (CR or PR) will be provided with an exact 95% 2-sided confidence interval calculated using a method based on the *F* distribution. For the definition of the response categories, see Appendix C.

6.2.2. Secondary Efficacy Parameters

The secondary efficacy parameters are:

The progression free survival.

After discontinuing the study medication, patients may be treated with additional therapy. Data collected after patients have been treated with additional therapy will not be used for efficacy analyses except for survival.

•

6.2.2.1. Secondary Analyses

6.2.2.1.1. Response Rate

The response rate (CR or PR) will be provided with an exact 95% 2-sided confidence interval calculated using a method based on the *F* distribution. For the definition of the response categories, see Appendix C.

6.2.2.1.2. Progression-free survival (PFS)

All patients who receive at least 1 dose of AG-013736 and have a baseline assessment of disease will be included in the analysis. Patients who were inadvertently enrolled (eg, patients who are

determined to have the incorrect histological cancer type after receiving a dose of medication, based on their screening disease assessment) will be excluded from analyses.

PFS is defined as the difference in days between the first date that criteria for progression were met or the patient died and the date of first dose of AG-013736. Since the day of first dose and the day criteria for progression were met (or the patient died) are each counted as a full day, 1 day will be added to each calculation. Patients lacking an evaluation of tumor response after their first dose will have their event time censored at 1 day. Patients not experiencing disease progression during the treatment and follow-up periods and who do not die during the treatment period will have their event time censored on the last study date that objective tumor assessments verified lack of disease progression.

An estimate of the PFS curve from the Kaplan-Meier¹² method will be presented. Median event time and a 2-sided 95% confidence interval for the median will be provided.¹³

Duration of Overall Response

Analyses on duration of overall objective response will be done for all patients achieving a PR or CR. Duration of overall objective response is defined as the difference in days between the first date criteria for progression occurred and the first date that criteria for a PR or CR were met. Since the day the criteria for PR or CR were met and the first day criteria for progression occurred are each counted as a full day, 1 day will be added to each calculation. Patients who achieve a PR or CR and who do not experience disease progression during the treatment and follow-up periods and who do not die during the treatment period will have their event time censored on the last study date that objective tumor assessments verified lack of disease progression. Patients who die during the treatment period with no disease progression observed, and still in response, will have their duration calculated using the date of death as a non-censored value. Patients who achieve a PR and then a CR will have times calculated using the date of the PR as the first day.

Estimates of duration of overall response from the Kaplan-Meier¹² method will be presented. Median event time (if appropriate) and a 2-sided 95% confidence interval for the median will be provided. ¹³ The number of CR and PR patients may be small and thereby limit use of the Kaplan-Meier method to provide reliable information. In this case, descriptive statistics or listings will be provided.

6.2.2.1.3. Survival

All patients who receive at least 1 dose of AG-013736 are eligible for this analysis. Survival time is the difference in days between the date of death and the date of first dose of AG-013736. Since the day of first dose and the day of death are each counted as a full day, 1 day will be added to each calculation. Patients not expiring will have their survival times censored on the last date of known contact that the patient was documented to be alive. Patients lacking data beyond the day of first dose will have their survival times censored at 1 day.

An estimate of the survival time curve from the Kaplan-Meier method will be presented. Median event time and a 2-sided 95% confidence interval for the median will be provided.

6.2.3. Analysis of Dropouts

Patients discontinuing the study over time will be summarized.

6.2.4. Safety Parameters

All patients who receive any study treatment will be included in the final summaries and listings of safety data. Summaries of AEs and other safety parameters will be provided as appropriate

Frequencies of patients experiencing at least one AE will be displayed by body system and preferred term according to MedDRA terminology. Detailed information collected for each AE will include: description of the event, duration, whether the AE was serious, intensity, relationship to study drug, action taken, and clinical outcome. Intensity (severity) of the AEs will be graded according to the CTCAEv4.0. Emphasis in the analysis will be placed on AEs classified as treatment emergent.

Summary tables will present the number of patients observed with AEs and corresponding percentages. The denominator used to calculate incidence percentages consists of patients receiving at least 1 dose of study medication. Within each table, the AEs will be categorized by MedDRA body system and preferred term. Additional subcategories will be based on event intensity and relationship to study drug.

Individual patient listings will be prepared for all AE data. Summary tables for extent of exposure to study medication will also be provided.

6.2.5. Clinical Laboratory Analysis

Listing tables will be prepared for each laboratory measure, and will be structured to permit review of the data by patient as they progress on treatment.

Summary tables will be prepared to examine the distribution of laboratory measures over time. Shift tables may be provided to examine the distribution of laboratory toxicities.

6.2.6. Analysis of Soluble Proteins

Plasma soluble protein will be assessed using 1 or more methods available at the time of the analyses. Possible technologies that are currently being explored include proprietary antibody coated analysis chips and laser excited mass spectroscopy. Plasma levels of soluble proteins (including but not limited to VEGF, placental growth factor [PIGF], and soluble VEGFR2 [sVEGFR2], and Thrombospondin-1) may be associated with angiogenesis or tumor physiology and may correlate with efficacy or biological activity. However, other unidentified proteins may also correlate. While samples will be taken on all patients, assays may only be performed if stage 2 is opened, otherwise, there will be insufficient clinical response to provide clinical correlates. Listing and summary tables will be prepared. Exploratory analyses will be done looking for changes in protein expression that predict for clinical response.

Protocol: 03/21/16

6.2.7. Gene Profiling

6.2.7.1. Tumor Samples

Tumor biopsy samples will be obtained when possible in order to develop primary tumor cell lines for studies directed at the identification of sensitive and resistant biomarkers. Gene profiles will be generated on cell lines using microarrays that have about 25,000 known genes. Exploratory analyses will be performed to detect changes to gene expression caused by treatment with AG-013736. Additional exploratory analyses will be performed to detect potential changes in gene expression that distinguish tumors that respond, or at least regress, from those that are stable or progressing.

Page 39 of 53

Data from the chip analysis will be processed by gene chip expression software. The intensity of each probe set of the array will be captured and expression values calculated using a scanner. Data analysis will be analyzed to identify genes that are differentially expressed between the baseline and treated tumor samples. Data analysis will be performed to identify genes that are differentially expressed on tumors that have responded (or at least regressed) and those that remained stable or progressed. The set of genes that may be associated with the clinical response will be further confirmed by RT-PCR method. In vitro cell cultures will also be tested for response to antiangiogenesis agents in vitro.

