2. STUDY OBJECTIVES

The primary objective of this study is to determine the activity of AG-013736 in metastatic melanoma as measured by the complete response (CR) and partial response (PR) by RECIST. A response will also be considered to have occurred if there is a >/= 25% reduction in the involved nodal basin specific uptake value (SUV) on PET/CT (see Appendix C). Secondary objectives are to:

- Progression free survival
- determine the safety profile of AG-013736
- determine duration of response
- determine overall survival
- obtain blood samples for population pharmacokinetic analyses
- explore relationships between clinical response and plasma soluble proteins
- explore relationships between clinical response with host and tumor genomics

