APPENDIX G PROCESSING OF SAMPLES FOR GENOMICS ANALYSIS

Pharmacogenomic analysis of tumor samples:

After the patient grants informed consent for the biopsy, at least a 4 mm cube of tumor tissue from a superficial lesion should be obtained by a punch, core, or excisional biopsy. The first portion of the tissue will be placed in lactated Ringer's solution and refrigerated at 4°C for up to 3 days. The remainder of the 4 mm cube should be snap frozen in liquid nitrogen within one hour and stored at -70°C to -80°C. After the patient signs informed consent for peripheral blood sample collection, a blood sample (5 mL) will be collected in purple cap EDTA tubes and stored at -20°C. At the request of Pfizer, samples should be shipped to the analysis laboratory in dry ice according to shipping instructions provided by the gene laboratory identified in the Study Manual. The samples will be stored in a secure environment until the analysis has been completed.

The tumor and peripheral blood samples will be used to analyze expression of RNA as they may relate to clinical response (tumor regression and/or toxicity) to AG-013736. No other studies will be performed with these samples.

Tumor RNA will be extracted and prepared by standard protocols used by the laboratory. From total RNA, cDNA will be generated by reverse transcription. The cDNA will be then fluorescently labeled and hybridized on Affymetrix Gene chips (microarrays) according to instructions provided by the manufacturer. These microarrays contain oligonucleotides representing about 25,000 known genes that represent most of the genes present in the human genome.

Data from the chip analysis will be processed by gene chip expression software. The intensity of each probe set of the array will be captured and expression values calculated using a scanner. Data analysis will be analyzed to identify genes that are differentially expressed between the baseline and treated tumor samples. Data analysis will be performed to identify genes that are differentially expressed on tumors that have responded (or at least regressed) and those that remained stable or progressed. The set of genes that may be associated with the clinical response will be further confirmed by RT-PCR method.

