The sample analysis will be anonymized and will be carried out specifically for the purposes of evaluating correlation of RNA patterns with clinical response. The samples will not be made available to anyone not associated with this study or external investigators. All materials (RNA) will be destroyed immediately after analysis. No genetic material will be stored. The samples will be identified by patient study identifier only and patient name, date of birth or other information will not be used on sample tube.

Axitinib (AG-013736) Neoadjuvant Melanoma Protocol Protocol: 03/21/16

Page 53 of 53

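### RT-PCR on the same patients' specimens verifies the array reading, not the association with response, so chance genes can be reported as confirmed

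*Combined protocol and SAP*

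**What the plan says.** Section 2 lists, among the secondary objectives, to "explore relationships between clinical response with host and tumor genomics".

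Section 6.2.7.1 describes an array screen: "Gene profiles will be generated on cell lines using microarrays that have about 25,000 known genes". One of its stated aims is to "identify genes that are differentially expressed on tumors that have responded (or at least regressed) and those that remained stable or progressed". The only later step given for the selected genes is: "The set of genes that may be associated with the clinical response will be further confirmed by RT-PCR method". Appendix G repeats that step.

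The two places differ on the material. Section 6.2.7.1 puts the arrays on cell lines grown from biopsies. Appendix G describes RNA taken from the tumor itself ("Tumor RNA will be extracted and prepared by standard protocols used by the laboratory") and gives the same array size: "These microarrays contain oligonucleotides representing about 25,000 known genes that represent most of the genes present in the human genome". Neither says which RNA the RT-PCR uses.

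Appendix G foresees no other sample set. It says "No other studies will be performed with these samples" and "All materials (RNA) will be destroyed immediately after analysis". Section 6.1.1.2 caps the trial at 32 treated patients, and the notes to the Schedule of Tests and Procedures make the tumor sample optional in Stage 1, so the number with tissue may be smaller.

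**The concern.** For each gene the question is whether expression is related to response, and the null is no relation. With about 25,000 genes and few responders, some genes will separate the two groups by chance. A confirmation step should remove most of them.

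RT-PCR on specimens from the same patients cannot do that. Patients, response labels and, to whatever extent the two assays agree, expression values are all carried over. If the few responders happened to express a gene highly on the array, they will tend to do so on RT-PCR. What the step can detect is a misread array value.

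At stake is how the tumor-genomics objective is read. Genes labelled as confirmed after this step would look better supported than they are, and the documents give no other safeguard against chance findings.

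**Working it through.** **Inputs from the documents.** About 25,000 genes (Section 6.2.7.1, Appendix G); at most 32 patients, 18 + 14 (Section 6.1.1).

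**Inputs assumed, because the documents give none.** Per-gene selection rule (top 20, or p below 0.05, 0.01 or 0.001); RT-PCR pass rule (p<0.05 two-sided, same direction as the array); array-to-PCR correlation ρ from 0.2 to 0.9; independent genes; ordinary t-tests; splits such as 4 responders against 28 non-responders.

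**1. The plan's own figures.** The gene analysis has no stated sample size or error rate. The Simon design that fixes the 32 patients reproduces: early stopping is 0.95^18 = 39.7% at a 5% response rate and 0.80^18 = 1.8% at 20%. The exact probability of a positive trial is 0.072 and 0.901 respectively. Nothing below touches that rule.

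**2. Chance genes entering the confirmation step.** Expected number = 25,000 × per-gene threshold: 1,250 at 0.05, 250 at 0.01, 25 at 0.001, 2.5 at 0.0001.

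**3. Re-measurement in the same patients.** Null expression X was simulated for 25,000 genes. The second assay was Y = ρX + √(1−ρ²) × noise in the same patients with the same labels. Top 20 null genes, 4 against 28:

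| ρ | Share passing RT-PCR | Of 20 genes |
|---|---|---|
| 0.2 | about 9% | about 2 |
| 0.3 | about 14–17% | about 3 |
| 0.5 | about 37–38% | about 7–8 |
| 0.7 | about 68–71% | about 14 |
| 0.8 | about 89% | about 18 |
| 0.9 | about 98% | about 20 |

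The lower correlations stand for different material on the two assays (cell line and tissue, or different time points); the higher ones stand for the same specimen. Ranges show Monte Carlo variation.

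**4. If a threshold rather than a top-20 list selects the genes** (4 against 28; share of selected null genes passing):

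| Selection | ρ = 0.7 | ρ = 0.8 | ρ = 0.9 |
|---|---|---|---|
| p<0.05 | 32% | 43% | 58% |
| p<0.01 | 51% | 63% | 89% |
| p<0.001 | 74% | 87% | 98% |

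Splits of 6/26, 10/22 and 4/12 give similar figures.

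**5. Benchmark.** In new patients a null gene passes p<0.05 in the given direction with probability 0.05/2 = 2.5%, or 20 × 0.025 = 0.5 of 20 genes. Simulation gave 1–4%.

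**6. A strict threshold.** At 0.05/25,000 = 2 × 10⁻⁶ per gene, only about 5–12% of null trials had any gene to send to RT-PCR.

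**7. False discovery control.** With Benjamini-Hochberg at 10% on t-test p-values, about 3–18% of null trials declared any gene (40 trials per setting), consistent with the nominal 10%.

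**8. Why the form of permutation matters.** Permuting labels separately for each gene cannot give a p-value below 1/C(32,4) = 1/35,960 for 4 against 28, or 1/C(18,3) = 1/816 for 3 against 15. Benjamini-Hochberg at 10% needs k genes with p ≤ 0.10k/25,000, so k ≥ 250,000 × p. At the floor this is 250,000/35,960 = 6.95, so 7 genes; or 250,000/816 = 306.4, so 307 genes. Gene-wise permutation is therefore too coarse with few responders.

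**The case against.** Several points on the other side have force.

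- **Which RNA.** A reader might infer that RT-PCR is run on the very tumor RNA that selected the genes. The text does not say so: one place profiles cell lines, the other tumor RNA, and tissue is taken at more than one time point. Destroying RNA after analysis does not identify the RT-PCR material either. What the documents support is the same patients' specimens. If the two assays use different material, the correlation and the pass rate are lower, as the first three rows of the top-20 table show. They still exceed 2.5%.
- **Whether chance genes will be confirmed.** A reader might infer that following the plan must produce a list of false genes. It need not: with a threshold near 2 × 10⁻⁶ few or none would reach RT-PCR. The plan states no threshold, so the supportable claim is that chance genes can be reported as confirmed.
- **Exploratory status.** Section 6.2.7.1 calls these analyses exploratory, Section 6.2 stresses estimation, and Section 6 leaves detailed methods to a separate Analysis Plan. This limits the consequence. It does not settle the point, because an exploratory screen may report unadjusted candidates, but here the selected set is to be called confirmed.
- **Ordinary laboratory meaning.** RT-PCR confirmation can be read as technical verification of the array. That is the right reading of what the step achieves. The sentence, however, ties it to genes that may be associated with response and offers no other test.

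**Conclusion.** The point holds in a limited form. The one step stated after the screen cannot test association with response, because no patients outside the trial's 32 are foreseen and no error-rate control is given.

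For a top-20 list with no true associations, roughly 10–40% of genes pass at correlations of 0.2–0.5 and roughly 70–98% at 0.7–0.9. Against 2.5% in new patients, that is about 4 to 16 times (10/2.5 to 40/2.5) and about 28 to 39 times (70/2.5 to 98/2.5). These figures rest on the assumed selection rule, pass rule, correlation, splits and gene independence. The direction of the problem does not depend on the exact values, but the number of false genes does.

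The consequence is confined to the exploratory biomarker conclusions. The Stage 1 and Stage 2 rules count clinical responses only and are unaffected.

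**What to change.** In Section 6.2.7.1 and Appendix G, replace the RT-PCR sentence with wording such as:

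*Genes associated with response will be declared at a false discovery rate of 10%, using Benjamini-Hochberg on moderated or ordinary t-test p-values, or permutation of response labels with the null distribution pooled across genes. RT-PCR on specimens from the same patients will be reported as technical verification of the array measurement only. Genes that pass will be reported as exploratory candidates that need an independent cohort.*

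The same edit should state which material each assay uses, so that the cell-line and tumor-RNA descriptions agree, and give the RT-PCR pass rule. It should be settled before expression data are compared with response.

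The cost is a wording change and a short analysis program, with no new patients, samples or assays. The downside is that the gene list will be shorter and may be empty.

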7. OVERSIGHT COMMITTEES

A UC Irvine data safety monitoring board will review safety data consisting of the reported adverse events, discontinuations and mortality that occur during the course of the protocol. The DSMB will evaluate the safety of the program using available data from the clinical and SAE databases on a 6 month basis, or more frequently if a safety issue arises. Based on the data review, the committee will make recommendations as to whether any modifications of the trial are warranted.

Page 40 of 53

Protocol: 03/21/16

APPENDIX B Other Administrative and Regulatory Procedures

1. INTRODUCTION

This appendix provides information necessary to administer this study in compliance with global Good Clinical Practices (GCPs), government regulations, and the policy and procedures of Pfizer Inc.

2. ADMINISTRATIVE PROCEDURES

2.1. Compliance With Good Clinical Practice and Ethical Considerations

This study must be conducted in compliance with Institutional Review Board/ Independent Ethics Committee (IRB/IEC), informed consent regulations, and International Committee on Harmonization (ICH) GCP Guidelines. In addition, all local regulatory requirements will be adhered to, in particular those which afford greater protection to the safety of the trial participants.

This study will be conducted in general according to the Declaration of Helsinki and with local laws and regulations relevant to the use of new therapeutic agents in the country of conduct.

Before initiating a trial, the investigator/institution will have written and dated approval/favorable opinion from the IRB/IEC for the trial protocol, written informed consent form, subject recruitment procedures (eg, advertisements), and data collection instruments which will be completed by subjects. Protocol amendments, consent form updates, and any amendments to the documents described before must be approved by the IRB/IEC prior to implementation unless such changes are necessary to address immediate safety concerns.

2.2. Informed Consent

The investigator, or a person designated by the investigator, will explain the benefits and risks of participation in the study to each subject, subject's legally acceptable representative (not permitted for Phase 1 normal volunteer studies) or impartial witness and obtain written informed consent prior to the subject entering the study (before initiation of protocol-specified procedures).

The informed consent form must be agreed to by Pfizer and the IRB/IEC and must be in compliance with ICH GCP and in accordance with local regulatory and legal requirements, in language readily understood by the subject. Each subject's original consent form, signed and dated by the subject or by the subject's legally acceptable representative, and a witness to the informed consent discussion, will be retained by the investigator.

2.3. Confidentiality of Subject Information

All subjects will be assigned a study subject number. Subsequently, subjects will be identified in the CRFs only by their initials and that number. Any information published as a result of the

study will be such that it will not permit identification of any subject. The information from this study will be available within Pfizer Inc and may be shared with the regulatory authorities. It may also be the subject of an audit by a regulatory agency (eg, FDA) within the local government. The subject's identity will remain protected except as required for legal or regulatory inquiries.

2.4. Institutional Review Board (IRB) or Ethics Committee (EC) Review and Approval of the Study

An IRB/EC, that is organized and operates according to GCP and applicable laws and regulations, should safeguard the rights, safety, and well-being of all trial subjects. No subject should be admitted to a trial before the IRB/EC issues its written approval/favorable opinion of the trial.

The investigator is responsible for:

- Promptly reporting to the IRB/EC all changes in the research activity and all unanticipated problems involving risks to human subjects or others;
- Submitting a progress report describing the status of the clinical investigation to the IRB/EC at appropriate intervals not exceeding 1 year. Copies of these reports will also be provided to Pfizer Inc;
- Submitting a final progress report to the IRB/EC (if requested) following completion, termination, or discontinuation of the study. Copies of these reports will also be provided to Pfizer Inc;
- Handling all communications with the IRB/EC regarding the study of a Pfizer Inc drug;
- Providing a copy of all communications from the IRB/EC to the investigator regarding its review of and initial approval of the study and its reapprovals to the Pfizer Inc Site Monitor; and
- Documenting and retaining in the institution the identification codes, names, and randomization numbers (where applicable) for all trial participants.

